## 7.2 Immune Evaluations

Plasma cytokines including TARC (CCL17), YKL40, eotaxin 3 (CCL26), IL-13, IL-4, Arg 1, Hyaluronan, soluble ST2 will be measured using the MILLIPLEX® MAP Human Cytokine/Chemokine/Growth 28 Factor Panels, and individual Simplex or ELISA kits (1 light green top with approximately 2 mL of anti-coagulated blood will be allotted for cytokine assessment).

## 8.0 REGISTRATION AND REQUIRED DATA

### 8.1 Protocol Registration

Subject must have been enrolled in HSR 210184. Subjects who are consented to the study must be registered in the Clinical Trials Office. All subjects who have signed an informed consent should have demographics and date of signed informed consent entered into the database.

### 8.2 Evaluations and Assessments

All evaluations and assessments should be completed as described in Study Timeline. Any assessments not described in detail below should be done according to standard of care practices.

### 8.3 Immune Evaluations

Plasma cytokines including TARC (CCL17), YKL40, eotaxin 3 (CCL26), IL-13, IL-4, Arg 1, Hyaluronan, soluble ST2 will be measured using the MILLIPLEX® MAP Human Cytokine/Chemokine/Growth 28 Factor Panels, and individual Simplex or ELISA kits (1 light green top with approximately 2 mL of anti-coagulated blood will be allotted for cytokine assessment).

### 8.4 Subject Status Definitions

- Enrolled: All subjects who sign an informed re-consent will be considered enrolled on the study. All subjects consented on the study must be entered into Clinical Trials Office Database.
- Note: The IRB defines any individual that has signed an informed consent as an enrollment in this study and so screen failures should be reported to the IRB with enrollment numbers.
- On-Study: A subject is considered on-study on the date when the study team has confirmed the subject has met all of the inclusion and none of the exclusion criteria;
- On Follow-up: A subject is considered on follow-up on the date that they have met any of the criteria in section 4.0.
- Off-Study: A subject is considered off-study if they are removed from the study for any of the reasons listed in section 4.0.

## 9.0 RISKS AND BENEFITS

---

Plasma cytokines will be measured using the MILLIPLEX® MAP Human Cytokine/Chemokine/Growth 28 Factor Panels, and individual Simplex or ELISA kits.

## **9.1 Potential Benefits of Follow up with Patient**

Subject recovery from COVID-19 is assessed by a Pulmonary and Critical Care attending working in clinic that day and are provided with recommendations based on any abnormalities found.

## **9.2 Potential risks**

1. Risks of PFTs: Dizziness, coughing, shortness of breath and/or provocation of asthma attack with deep inhalation during testing.
2. Risks of HRCT scan: radiation exposure, harm to unborn children
3. Risks of phlebotomy: local discomfort, bruising and/or hematoma, bleeding, fainting, infection.
4. Total blood draws will not exceed 5 mL

## **9.3 Alternatives**

Follow up as needed with primary care physician.

## **10.0 ADVERSE EVENTS AND SAFETY EVALUATION**

Adverse events will be evaluated and scored using Division of AIDS (DAIDS) Table for Grading the Severity of Adult and Pediatric Adverse Events Version 2.1 (DAIDS v2.1).

(<https://rsc.niaid.nih.gov/sites/default/files/daidsgradingcorrectedv21.pdf>)

### **10.1 Adverse Event (AE)**

An adverse event will be considered any undesirable sign, symptom, medical, or psychological condition even if the event is not considered to be related to the investigational drug/intervention. Medical condition/diseases present before starting the investigational drug/intervention will be considered adverse events only if they worsen after starting study treatment/intervention. An adverse event is also any undesirable and unintended effect of research occurring in human subjects as a result of the collection of identifiable private information under the research. Adverse events also include any problems associated with the use of an investigational drug that adversely affects the rights, safety or welfare of subjects.

### **10.2 Serious Adverse Event (SAE)**

An adverse event (AE) is considered a serious adverse event (SAE) if, in the view of either the investigator or sponsor, it results in any of the following outcomes:

- death,
- a life-threatening adverse event,
- inpatient hospitalization or prolongation of existing hospitalization,
- a persistent or significant incapacity or substantial disruption of the ability to conduct normal life functions, or
- a congenital anomaly/birth defect

Important medical events that may not result in death, be life-threatening, or require hospitalization may be considered serious when, based upon appropriate medical judgment, they may jeopardize the participant and may require medical or surgical intervention to prevent one of the outcomes listed in this definition. Examples of such medical events include allergic bronchospasm requiring intensive treatment in an emergency room or at home, blood dyscrasias or convulsions that do not result in inpatient hospitalization, or the development of drug dependency or drug abuse.

### **10.3 Unexpected Adverse event: (UAE)**

The PI will be responsible for determining whether an AE is expected or unexpected. An AE will be considered unexpected if the nature, severity, or frequency of the event is not consistent with the risk information previously described for the study intervention.

#### **10.4 Unanticipated Problem (UP)**

The Office for Human Research Protections (OHRP) considers unanticipated problems (UPs) (may include a data breach) involving risks to participants or others to include, in general, any incident, experience, or outcome that meets all of the following criteria:

- Unexpected in terms of nature, severity, or frequency given the research procedures that are described in the protocol-related documents, such as the Institutional Review Board (IRB)-approved research protocol and informed consent document; and (b) the characteristics of the participant population being studied;
- Related or possibly related to participation in the research ("possibly related" means there is a reasonable possibility that the incident, experience, or outcome may have been caused by the procedures involved in the research); and
- Suggests that the research places participants or others at a greater risk of harm (including physical, psychological, economic, or social harm) than was previously known or recognized.

#### **10.5 Protocol Deviation**

A protocol deviation is defined as any change, deviation, or departure from the study design or procedures of a research project that is NOT approved by the institution's IRB prior to its initiation or implementation, OR deviation from standard operating procedures, Good Clinical Practices (GCPs), federal, state or local regulations. Protocol violations may or may not be under the control of the study team or UVA staff. These protocol violations may be major or minor violations.

#### **10.6 Reporting Interval**

All AEs and SAEs will be documented from the first administration of study product and for the following 60 days or until un-enrollment from the study, whichever comes sooner. All AEs and SAEs will be followed until resolution even if this extends beyond the study-reporting period. Resolution of an adverse event is defined as the return to pre-treatment status or stabilization of the condition with the expectation that it will remain chronic.

#### **10.7 Investigator's Assessment of Adverse Events**

The determination of seriousness, severity, and causality will be made by an on-site investigator who is qualified (licensed) to diagnose adverse event information, provide a medical evaluation of adverse events, and classify adverse events based upon medical judgment. This includes but is not limited to physicians, physician assistants, and nurse practitioners. The study PI will review events that occur at the time of occurrence.

#### **10.8 Assessment of Severity**

For AEs not included in the protocol-defined grading system, the following guidelines will be used to describe severity.

- **Mild** – Events require minimal or no treatment and do not interfere with the participant's daily activities.
- **Moderate** – Events result in a low level of inconvenience or concern with the therapeutic measures. Moderate events may cause some interference with functioning.
- **Severe** – Events interrupt a participant's usual daily activity and may require systemic drug therapy or other treatment. Severe events are usually potentially life-threatening or incapacitating. Of note, the term "severe" does not necessarily equate to "serious".

#### **10.9 Assessment of Association**

All AEs must have their relationship to study intervention assessed by the clinician who examines and evaluates the participant based on temporal relationship and his/her clinical judgment. The degree of certainty about causality will be graded using the categories below.

- **Definitely Related** – There is clear evidence to suggest a causal relationship, and other possible contributing factors can be ruled out. The clinical event, including an abnormal laboratory test result,

occurs in a plausible time relationship to study intervention administration and cannot be explained by concurrent disease or other drugs or chemicals.

- **Probably Related** – There is evidence to suggest a causal relationship, and the influence of other factors is unlikely. The clinical event, including an abnormal laboratory test result, occurs within a reasonable time after administration of the study intervention, is unlikely to be attributed to concurrent disease or other drugs or chemicals.
- **Possibly Related** – There is some evidence to suggest a causal relationship (e.g., the event occurred within a reasonable time after administration of the trial medication). However, other factors may have contributed to the event (e.g., the participant's clinical condition, other concomitant events).
- **Unlikely to be related** – A clinical event, including an abnormal laboratory test result, whose temporal relationship to study intervention administration makes a causal relationship improbable (e.g., the event did not occur within a reasonable time after administration of the study intervention) and in which other drugs or chemicals or underlying disease provides plausible explanations (e.g., the participant's clinical condition, other concomitant treatments).
- **Not Related** – The AE is completely independent of study intervention administration, and/or evidence exists that the event is definitely related to another etiology.

## 11.0 REPORTING ADVERSE EVENTS AND PROTOCOL DEVIATIONS

All AEs meeting DAIDS grade 3 severity or above including local and systemic reactions not meeting the criteria for SAEs will be captured. Information to be collected includes event description, time of onset, clinician's assessment of severity, relationship to study product (assessed only by those with the training and authority to make a diagnosis), and time of resolution/stabilization of the event. All AEs meeting DAIDS grade 3 severity or above occurring while on study must be documented appropriately regardless of relationship. All AEs meeting DAIDS grade 3 severity or above will be followed to adequate resolution.

Any medical condition (including a laboratory abnormality) that is present at the time that the participant is screened will be considered as baseline and not reported as an AE. However, if the study participant's condition deteriorates at any time during the study, it will be recorded as an AE.

Changes in the severity of an AE will be documented to allow an assessment of the duration of the event at each level of severity to be performed. AEs characterized as intermittent require documentation of onset and duration of each episode.

AEs meeting DAIDS grade 3 severity or above must be recorded into the case report forms and will be reported per the following guidelines (**Error! Reference source not found.2**).

It is the responsibility of the principal investigator to use continuous vigilance to prevent, identify and report protocol deviations. Major protocol deviations must be reported to the UVA IRB-HSR per the following guidelines (Table 2). Minor deviations do not need to be reported to the UVA IRB-HSR. All deviations must be addressed in study source documents.

**Table 2**

Type of Event	To whom will it be reported:	Time Frame for Reporting	How reported?
---------------	------------------------------	--------------------------	---------------

Any internal event resulting in death that is deemed DEFINITELY related to (caused by) study participation	IRB-HSR	Within 24 hours	IRB Online and phone call www.irb.virginia.edu/
Internal, Serious, Unexpected adverse event All adverse events deemed to be related to the drug meeting DAIDS severity grade 3 and above will be reported.	IRB-HSR	Within 7 calendar days from the time the study team received knowledge of the event.	IRB Online www.irb.virginia.edu/
Unanticipated Problems that are not adverse events or protocol deviations This might include a Data Breach.	IRB-HSR	Within 7 calendar days from the time the study team received knowledge of the event.	Unanticipated Problem report form. Unanticipated Problem Report Form
Protocol Deviations/Noncompliance	IRB-HSR	Within 7 calendar days from the time the study team received knowledge of the event.	Protocol Deviation, Noncompliance and Protocol Exception Reporting Form Protocol Deviation Protocol Exception Reporting Form
Data Breach	The UVa Corporate Compliance and Privacy Office  ITC: if breach involves electronic data  Police if breach includes items that are stolen:	As soon as possible and no later than 24 hours from the time the incident is identified.  As soon as possible and no later than 24 hours from the time the incident is identified.  IMMEDIATELY.	UVa Corporate Compliance and Privacy Office- [contact]  ITC: Information Security Incident Reporting procedure , https://security.virginia.edu/report-information-security-incident

	
Stolen on UVA Grounds
 
OR
 
Stolen off UVA Grounds- contact police department of jurisdiction of last known location of PHI
		UVa Police-Phone- [contact]
--	---	--	----------------------------------

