## 5.2 Known potential risks

1. PFT: Dizziness, coughing, shortness of breath and/or provocation of asthma attack with deep inhalation during testing.
2. HRCT scan: radiation exposure, harm to unborn children.
3. Phlebotomy: local discomfort, bruising and/or hematoma, bleeding, fainting, infection. Total blood draw not to exceed 5mL.

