## 13.0 STOPPING DECISION RULES

The study enrollment will be stopped and reviewed by the PI if any of the following specific events occur or, if in the judgement of the study physician, subject safety is at risk of being compromised during the visit:

- Death due to study procedure
- Occurrence of a life threatening allergic/hypersensitivity reaction (anaphylaxis), manifested by bronchospasm with or without urticaria or angioedema requiring hemodynamic support with pressor medications or mechanical ventilation due to any of the study procedures performed (pulmonary function testing, blood collection)
- One subject with a grade 4 or persistent grade 3 ( $\geq 72$  hours) associated with study procedures

- Two subjects with persistent Grade 3 ( $\geq$  72 hours) or higher lab toxicity for the same parameter associated with study procedures
- An overall pattern of symptomatic, clinical, or laboratory events that the study investigators consider associated with study product and that may appear minor in terms of individual events but that collectively may represent a serious potential concern for safety.
- Any other event(s) which is considered to be a serious adverse event in the good clinical judgment of the attending physician team. This will be appropriately documented.

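### Adverse-event wording written for the parent trial's drug was carried into a procedure-only extension, so some expected serious procedure events have no explicit route to the IRB-HSR and the adverse-event window closes before the only visit

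*Protocol*

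**What the plan says.** The visit in Protocol section 5.0 consists of a urine pregnancy test, a blood draw, a non-contrast chest CT, lung function and walk testing, and questionnaires. No drug is given. Section 5.2, repeated in 9.2, lists three groups of risk: HRCT, phlebotomy, and the first item, "PFT: Dizziness, coughing, shortness of breath and/or provocation of asthma attack with deep inhalation during testing".

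The adverse-event text uses several different reference exposures:

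- **Table 2, death row.** Covers "Any internal event resulting in death that is deemed DEFINITELY related to (caused by) study participation". It is not tied to the drug. Report within 24 hours.
- **Table 2, second row.** The heading is "Internal, Serious, Unexpected adverse event" and names no cause. Report within 7 calendar days. Beneath it stands the sentence "All adverse events deemed to be related to the drug meeting DAIDS severity grade 3 and above will be reported".
- **Table 2, Unanticipated Problems row.** Restricted to problems "that are not adverse events or protocol deviations".
- **Section 10.3.** The PI decides expectedness: "An AE will be considered unexpected if the nature, severity, or frequency of the event is not consistent with the risk information previously described".
- **Section 10.9.** The top causality grade requires that the event "occurs in a plausible time relationship to study intervention administration". The example under the possibly related grade is timed from the trial medication.
- **Section 11.0.** Events of DAIDS grade 3 or above are recorded whatever their cause for as long as the participant is on study, but the relationship item collected is to study product.
- **Section 10.6.** Documentation runs from first study product for 60 days, or to un-enrollment if sooner.
- **Section 13.0.** Most stopping triggers refer to study procedures, for example "One subject with a grade 4 or persistent grade 3" associated with them. Review is by the PI.

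**The concern.** Section 13.0 shows that the authors recognised the change of exposure from drug to procedures. Sections 10.6, 10.9 and 11.0 and the second row of Table 2 were not brought into line with it.

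Three things follow. The one sentence that would send grade 3 or higher events to the IRB-HSR irrespective of expectedness covers none of the extension's listed risks. No data item records whether an event was caused by a procedure, so the study cannot cleanly tabulate the harm of its own visit. And read literally, the documentation window excludes the visit altogether. The same event could halt enrollment under section 13.0 while no line of Table 2 calls for a report, with the PI both deciding expectedness and reviewing the stop.

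**Working it through.** No power, alpha or event-rate figure bears on this point, and the plan states no figure to reproduce. The check is a trace through Table 2, followed by day arithmetic.

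**1. Trace of serious procedure-caused events.** Classify these events by outcome (death graded definitely related; death graded lower; non-fatal) and by expectedness (expected; unexpected): 3 × 2 = 6 types. Apply each row of Table 2 under two readings of the second row. Under reading A the drug sentence adds to the heading. Under reading B it limits the heading to drug-related events.

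| Event type | Reading A | Reading B |
|---|---|---|
| Death, definitely related, expected | death row | death row |
| Death, definitely related, unexpected | death row | death row |
| Death, graded lower, expected | none | none |
| Death, graded lower, unexpected | second-row heading | none |
| Non-fatal, expected | none | none |
| Non-fatal, unexpected | second-row heading | none |

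Reading A: 4 of 6 types have a route and 2 do not. Reading B: 2 of 6 have a route and 4 do not. These are counts of event types, not frequencies. The documents give no rate for any of them.

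The Unanticipated Problems row does not help, because it excludes adverse events. The general definition in section 10.4 would not rescue the expected types either, since it requires the problem to be unexpected.

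**2. Example.** A participant is admitted after an asthma attack provoked by lung function testing. Admission makes the event serious (section 10.2). The death row does not apply. The second-row heading applies only if the event is unexpected, and the nature of the event is a listed risk. The added sentence does not apply, because no drug caused it. If the PI judges the event expected, no row calls for a report. If the PI judges its severity to exceed what was described, it goes to the IRB-HSR within 7 days.

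**3. Reference exposures in section 13.0.** Of its six listed triggers, four name a study procedure, one names study product and one (a serious event in the physicians' judgment) names no cause.

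**4. Documentation window.** Inputs: 60 days from first study product (section 10.6); visit at Day 365 ± 90 after enrollment (section 5.0). Assumption: first dose at about enrollment.

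- Earliest visit: 365 − 90 = Day 275. Latest: 365 + 90 = Day 455.
- Gap from window close to visit: 275 − 60 = 215 days at the least, 455 − 60 = 395 days at the most.
- For the window to reach even the earliest visit, first dosing would have to be no sooner than Day 275 − 60 = Day 215 after enrollment. The un-enrollment clause can only shorten the window.

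Section 10.6 read literally therefore covers no event at the visit, while section 11.0 requires grade 3 or higher events on study to be documented. The two conflict.

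**5. Numbers exposed.** Section 6.2: 40 enrolled − 7 deaths by Day 60 = 33 at most, each with one visit.

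**The case against.** A reader might infer that expedited reporting as a whole is tied to the drug, so that a serious procedure-caused event reaches nobody outside the study team. The documents do not support that. The death row speaks of study participation, and the second-row heading names no cause. On its plain reading, serious unexpected procedure events go to the IRB-HSR within 7 days. Section 10.3 also lets an event be unexpected by severity or frequency, and the listed risk puts an asthma attack beside dizziness and coughing without mentioning admission. A hospitalized attack could well be judged unexpected and reported. The gap in the example depends on the PI deciding the other way.

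A reader might also infer that section 10.9 forces a visit-day event down to unlikely or not related because dosing was about a year before. That too goes beyond the text. The scale refers to the study intervention and to clinical judgment. Section 10.1 speaks of drug/intervention, which can be read to include procedures, and the trial medication appears in 10.9 only inside an example. Mis-grading is a risk of the wording, not its stated result.

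Other text softens the point. Section 11.0 requires grade 3 or higher events to be recorded and reported, though under the guidelines of Table 2, which leads back to the same rows. Monitoring visits (section 14.4) and post-approval monitoring (section 12.1) give outside sight of the records. Post-approval selection is at random or on request, and neither mechanism is described as triggered by an event.

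What stands after this is narrower but definite: the two event types with no explicit route under either reading, the unresolved meaning of the second row, the missing procedure-relationship item, and the conflict between sections 10.6 and 11.0.

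**Conclusion.** The point holds as an internal inconsistency with a narrow reporting gap. Under the reading most favourable to the plan, 2 of 6 types of serious procedure event lack an explicit route to the IRB-HSR: expected non-fatal events, and expected deaths graded below definitely related. If the drug sentence limits its row, the count is 4 of 6. Separately, the section 10.6 window closes 215 to 395 days before the visit, assuming dosing near enrollment.

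The practical scale is small: one visit, low-intensity procedures, at most 33 participants, and no efficacy endpoint affected. The number of events that would go unreported cannot be estimated from the documents. Nor can the IRB-HSR's own reporting rules be seen here, and they may already require more than Table 2 states. The case for acting is that the text contradicts itself on safety and the correction is only wording.

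**What to change.** Reconcile Protocol sections 10.6, 10.9, 11.0 and 13.0 with Table 2 in one edit.

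- **Table 2, second row.** After the reference to the drug, add *or to a study procedure*, and state that the sentence adds to the heading. The drug wording should stay: section 6.1 still defines a safety population by dosing, and one section 13.0 trigger still refers to study product. This gives the two open event types a route when the event is grade 3 or above and is judged related to a procedure.
- **Sections 10.9 and 11.0.** Record and grade relationship to study procedures (PFT/6MWT, CT, phlebotomy) as well as to study product.
- **Section 10.6.** Make the documentation window cover the extension visit, in agreement with section 11.0.
- **Section 13.0.** State whether an event that meets one of its rules is notified to the IRB-HSR, consistently with Table 2. Whether every such event should go within 7 days is a policy choice for the sponsor and the IRB-HSR. The documents do not settle it.

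The cost is revised wording in these sections, one added relationship item on the case report form, and at most a few extra IRB reports in up to 33 participants.
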